15.2 Correlative Studies

15.2.1 Blood correlative studies

The following samples will be collected:

- A. 10 cc blood will be collected for isolation of plasma at screening (or baseline as per study calendar), 8, and 15 weeks and stored in 500 ul aliquots at -80C.
- B. Blood will be collected in TruCulture system 1 ml tubes containing either LPS or media at screening, 8, and 15 weeks. Within 15 minutes of the blood draw the samples should be incubated at 37C for 24-48 hours, then the supernatant will be isolated and stored in 250 ul aliquots. (instructions for blood processing: https://myriadrbm.com/products-services/truculture/truculture-video/)

Samples will be collected at the time of standard of care phlebotomy whenever possible. Patients will fast for at least 8 hours prior to phlebotomy whenever possible. The study coordinator will record time of blood draw and whether or not patient was fasting.

15.2.2 Correlative analyses

Thawed samples will be batch-analyzed for estrogens, high sensitivity C reactive protein, and a panel of pro-inflammatory (e.g., IL-6, IL-1, TNF- α , IL-17) and regulatory cytokines (e.g., IL-10) using high sensitivity tandem mass spectroscopy-based, immunoturbidimetric, and multiplex assays, respectively.⁶⁰ Stimulated cytokine and chemokine analysis will be performed using the TruCulture system.

16 ETHICAL AND REGULATORY CONSIDERATIONS

16.1 Informed consent

Informed consent will be obtained from all research participants prior to performing any study procedures using the most recent IRB-approved version.

16.2 Human Subjects Protections

16.2.1 Rationale for Subject Selection

This clinical trial is open to all patients with AIMSS with minimal restrictions in order to permit inclusion of as broad a population as possible. Only patients who read English will be enrolled because not all of the patient reported questionnaires have been linguistically validated in other languages.

16.2.2 Participation of Children

Patients must be at least 18 years of age to participate.

16.3 Institutional Review

Before implementing this study, the protocol, the proposed informed consent form and other information to be provided to subjects, must be reviewed and approved by a properly constituted IRB. Any amendments to the protocol must be reviewed and approved by the IRB.

16.4 Data and Safety Monitoring Plan

This study will be monitored in accordance with the NCI approved University of Michigan Rogel Cancer Center Data and Safety Monitoring Plan.

The study team will meet quarterly or more frequently depending on the activity of the protocol. The discussion will include matters related to the safety of study participants (SAE/UaP reporting), validity and integrity of the data, enrollment rate relative to expectations, characteristics of participants, retention of participants, adherence to the protocol (potential or real protocol deviations) and data completeness. At these regular meetings, the protocol specific Data and Safety Monitoring Report form will be completed and signed by the Principal Investigator or by one of the co-investigators.

Data and Safety Monitoring Reports will be submitted to the University of Michigan Rogel Cancer Center Data and Safety Monitoring Committee (DSMC) on a quarterly basis for independent review.

16.5 ADVERSE EVENTS

16.5.1 Experimental Therapy

For the most recent safety update, please refer to the current Study Agent Prescribing Information.

16.5.2 Adverse Event Reporting Requirements

Adverse event (AE) monitoring and reporting is a routine part of every clinical trial and is done to ensure the safety of subjects enrolled in the studies as well as those who will enroll in future studies using similar agents. Data on adverse events will be collected from the time of the initial study treatment through 30 days after the last dose of study treatment. Any serious adverse event that occurs more than 30 days after the last study treatment and is considered related to the study treatment must also be reported. Serious Adverse Events (SAEs) will continue to be followed until:

- Resolution or the symptoms or signs that constitute the serious adverse event return to baseline;
- There is satisfactory explanation other than the study treatment for the changes observed; or
- Death.

The investigator is responsible for the detection, documentation, grading and assignment of attribution of events meeting the criteria and definition of an AE or SAE. The definitions of AEs and SAEs are given below. It is the responsibility of the principal investigator to ensure that all staff involved in the trial is familiar with the content of this section.

Any medical condition or laboratory abnormality with an onset date before initial study treatment administration is considered to be pre-existing in nature. Any known pre-existing conditions that are ongoing at time of study entry should be considered medical history.

All events meeting the criteria and definition of an AE or SAE, as defined in Section 8.3, occurring from the initial study treatment administration through 30 days following the last dose of the study treatment must be recorded as an adverse event in the patient's source documents and on the CRF regardless of frequency, severity (grade) or assessed relationship to the study treatment.

In addition to new events, any increase in the frequency or severity (i.e., toxicity grade) of a pre-existing condition that occurs after the patient begins study treatment is also considered an adverse event.

16.5.3 Definitions

1. Adverse Event

An adverse event (AE) is any untoward medical occurrence in a patient receiving study treatment and which does not necessarily have a causal relationship with this treatment. An AE can be any unfavorable and unintended sign (including an abnormal laboratory finding), symptom, or disease temporally associated with the use of an experimental intervention, whether or not related to the intervention.

• Diagnostic and therapeutic non-invasive and invasive (i.e., surgical) procedures will not be reported as adverse events. However, the medical condition for which the procedure was performed must be reported if it meets the definition of an adverse event unless it is a preexisting (prior to protocol treatment) condition.

• Symptoms of the original or targeted disease are not to be considered adverse events for this study. The following symptoms are indicative of underlying disease (breast cancer) or its treatment and will not be reported as adverse events (unless the event is considered serious):

• AI-associated arthralgias (will be collected on patient-reported questionnaires)

• Symptoms and signs due to prior treatments (chemotherapy, radiation therapy, surgery)

• Adverse events related to disease progression

• Hospitalization or treatment related to breast surgery or breast reconstruction procedures

• Abnormal laboratory values or test results constitute adverse events if they induce clinical signs or symptoms or require therapy. They are to be captured under the signs, symptoms or diagnoses associated with them.

1. Serious Adverse Event

An adverse event is considered "serious" if, in the view of the investigator, it results in any of the following outcomes:

o Death

If death results from (progression of) the disease, the disease should be reported as event (SAE) itself.

• A life-threatening adverse event

An adverse even is considered 'life-threatening' if, in the view of either the investigator, its occurrence places the patient or subject at immediate risk of death. It does not include an adverse event that, had it occurred in a more severe form, might have caused death.

- Inpatient hospitalization or prolongation of existing hospitalization for ≥ 24 hours.
- A persistent or significant incapacity or substantial disruption of the ability to conduct normal life functions
- o A congenital anomaly/birth defect
- Important medical event

Any event that may not result in death, be life-threatening, or require hospitalization may be considered serious when, based upon appropriate medical judgment, they may jeopardize the patient and may require medical or surgical intervention to prevent one of the outcomes listed in this definition of "Serious Adverse Event". Examples of such medical events include allergic bronchospasm requiring intensive treatment in an emergency room or at home; convulsions that do not result in inpatient hospitalization or the development of drug dependency or drug abuse.

Previously planned (prior to signing the informed consent form) surgeries should not be reported as SAEs unless the underlying medical condition has worsened during the course of the study. Preplanned hospitalizations or procedures for preexisting conditions that are already recorded in the patient's medical history at the time of study enrollment should not be considered SAEs. Hospitalization or prolongation of hospitalization without a precipitating clinical AE (for example, for the administration of study therapy or other protocol-required procedure) should not be considered SAEs. However, if the preexisting condition worsened during the course of the study, it should be reported as an SAE.

2. Expected Adverse Events

An adverse event (AE) is considered "expected" if:

- For approved and marketed drugs, those adverse events are described in the approved Package Insert (Label).
- For investigational new drugs, those adverse events are described in the FDA Investigator's Brochure.
- In clinical research studies, information on expected adverse events is also summarized in the protocol and in the consent document. See section 9.1 for the list of expected adverse events related to the drug under study.

3. Unexpected Adverse Event

An adverse event (AE) is considered "unexpected" if it is not described in the Package Insert, Investigator's Brochure, in published medical literature, in the protocol, or in the informed consent document.

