5 ELIGIBILITY CRITERIA

5.1 Inclusion Criteria Yes/No (Response of "no" = patient ineligible)

- **5.1.1** Female subject aged ≥ 18 years who is postmenopausal according to standard clinical criteria (see section 8.3) or who has been receiving concomitant LHRH agonist therapy.
- **5.1.2** Taking the currently prescribed aromatase inhibitor therapy (anastrozole, exemestane, or letrozole) for adjuvant treatment of breast cancer or for chemoprevention for at least 3 weeks and no more than 2 years at the time of enrollment.
- **5.1.3** Planning to take the same AI therapy for at least 15 weeks.
- **5.1.4** New or worsening joint pain and/or myalgias since starting the AI therapy, with *worst* pain score of at least 4 out of 10 on the BPI over the 7 days prior to enrollment.
- **5.1.5** Completion of surgery (mastectomy or lumpectomy/partial mastectomy) for treatment of breast cancer at least 3 months prior to enrollment. Completion of axillary surgery as indicated (not required).
- **5.1.6** Completion of chemotherapy, if given. Concurrent use of LHRHa therapy, anti-HER2 therapy, bisphosphonate therapy, PARP inhibitor therapy, and CDK4/6 inhibitor therapy is permitted.
- **5.1.7** Patients receiving treatment with NSAIDs, acetaminophen, opioids, duloxetine, gabapentin, and/or pregabalin must have been taking a stable dose for at least 30 days prior to enrollment if they plan to continue the drug during study participation. If they do not plan to take the medication during study participation, they should stop the medication at least 7 days before initiation of study treatment.
- **5.1.8** _____ ECOG Performance Status 0-2.
- **5.1.9** Able to self-complete questionnaires in English.
- **5.1.10** Able to provide informed consent and willing to sign an approved consent form that conforms to federal and institutional guidelines.

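### The exclusion of non-serious symptoms due to prior cancer treatment (16.5.3) makes no exception for worsening and so conflicts with the worsening rule in 16.5.2

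*Combined protocol and SAP*

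**What the plan says.** Section 16.5.3 (Definitions, Adverse Event) begins broadly. An adverse event is any untoward sign, symptom or disease "temporally associated with the use of an experimental intervention, whether or not related to the intervention". The section then lists items, described as indicative of the breast cancer or its treatment, that "will not be reported as adverse events (unless the event is considered serious". One of them is "Symptoms and signs due to prior treatments (chemotherapy, radiation therapy, surgery". The bullet has no condition on when the symptom began or whether it has changed.

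Section 16.5.2 (Adverse Event Reporting Requirements) has two relevant sentences. The recording rule covers "All events meeting the criteria and definition of an AE or SAE, as defined in Section 8.3", and requires entry "regardless of frequency, severity (grade) or assessed relationship to the study treatment". The next sentence adds that, besides new events, "any increase in the frequency or severity (i.e., toxicity grade) of a pre-existing condition that occurs after the patient begins study treatment" is an adverse event too.

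Safety and tolerability is secondary objective 3 in Section 1.2. Section 12.3.2 (Secondary endpoints, item 4) plans descriptive reporting of adverse events, stratified by dose. Section 16.5.4 provides a five-level attribution scale that includes *Unlikely* and *Unrelated*.

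**The concern.** Two staff members could handle the same worsened symptom differently, each with the protocol behind them. One follows the worsening sentence and records it; the other follows the bullet and does not.

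The bullet also places a judgement of cause ahead of recording. An event that is recorded and marked *Unrelated* can be re-examined later. An event left off the case report form because someone thought it came from chemotherapy leaves no adverse event entry to revisit. The trial has a single arm, so no control group would show uneven recording.

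Some of the symptoms exposed to this judgement are non-specific, and Section 3.1.4 (Clinical Safety) lists them as reactions to CBD: fatigue, lethargy and decreased appetite. Most participants will have had at least one of the named treatments, because 5.1.5 asks for "Completion of surgery (mastectomy or lumpectomy/partial mastectomy) for treatment of breast cancer at least 3 months prior to enrollment".

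**Working it through.** The plan gives no figure on this point, so the main check is a comparison of the texts.

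| Situation after the first CBD dose (non-serious) | Section 16.5.2 | Prior-treatment bullet in 16.5.3 |
|---|---|---|
| Prior-treatment symptom, unchanged from before the first dose | Medical history, not an event | Not reported |
| Prior-treatment symptom, higher grade or frequency | Adverse event (worsening sentence) | Not reported |
| New symptom, judged due to prior treatment | Recorded if it meets the definition | Not reported |
| New symptom, judged possibly due to CBD | Recorded | Outside the bullet, so recorded |

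**Row 1.** The sections agree.

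**Row 2.** They contradict each other. The worsening sentence carries no condition about cause, and the bullet carries no condition about change. For serious events, by contrast, 16.5.3 does say that a pre-existing condition that worsened during the study must be reported. The non-serious list has no matching words.

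**Row 3.** The recording rule in 16.5.2 reaches only events that meet the definition, and the bullet sits inside that definition. The tension is therefore within 16.5.3: its general definition disregards relationship to the intervention, while the bullet lets a judgement of cause decide whether the event is reported at all.

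**Row 4.** The sections agree.

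**Can worsening be established?** The study calendar (Section 9) shows no adverse event assessment at screening or baseline, and Section 10.1 takes medical history from the record. The protocol therefore specifies no graded baseline for symptoms in general.

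**The pointer.** The recording rule sends the reader to Section 8.3 for the definitions. Section 8.3 is Contraception; the definitions are in 16.5.3.

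**Size.** If a reaction has true rate *r* among *n* patients and a share *f* of its events is dropped, the table is expected to show *n × r × (1 − f)* events. Only *n* = 44 (Section 4.2) comes from this trial's plan. As an assumption, take *r* from the fatigue row of Section 3.1.4: 11% at 10 mg/kg/day and 12% at 20 mg/kg/day (placebo 4%). The top dose here is 200 mg/day, which is 200/50 = 4 mg/kg/day at 50 kg and 200/80 = 2.5 mg/kg/day at 80 kg. The borrowed rates thus come from doses 10/4 = 2.5 to 20/2.5 = 8 times higher. Nothing in the documents informs *f*, so the full range is shown.

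| Share dropped *f* | Expected in table, *r* = 11% | Expected in table, *r* = 12% |
|---|---|---|
| 0% | 44 × 0.11 = 4.84 | 44 × 0.12 = 5.28 |
| 50% | 2.42 | 2.64 |
| 100% | 0 | 0 |

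This shows how the count would respond. It does not estimate what will happen.

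**The case against.** The best defence is that the two sections can be read together: the bullet means stable after-effects of earlier treatment, and the worsening sentence on the preceding page supplies the limit. That may well be what was intended. But the bullet does not say so, and it does state its one exception, for serious events. The defence therefore supports clarifying the text rather than leaving it.

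Other points for the plan stand, and they rule out stronger readings that a reader might infer.

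- *That 16.5.2 is a free-standing rule to record everything, which the bullet breaks.* The words "regardless of frequency, severity (grade) or assessed relationship to the study treatment" apply only to events that already meet the definition. The direct contradiction with 16.5.2 is the worsening sentence alone.
- *That all new CBD toxicity escapes.* A symptom is excluded only if it is attributed to chemotherapy, radiation or surgery. One judged possibly due to CBD remains reportable. So does fatigue put down to the aromatase inhibitor, the cause that Section 2.2 itself suggests, because that drug is not among the treatments named in the bullet.
- *That every participant is exposed.* Criterion 5.1.2 also admits women on chemoprevention, and surgery must be at least 3 months past. Having had surgery does not make it a plausible cause of new fatigue.
- *That fatigue is lost to the trial.* PROMIS measures it at baseline and weeks 4, 8 and 15, and change is summarised and modelled. That yields a mean score change rather than graded events by dose, but it is a real safeguard. Lethargy and decreased appetite have no PROMIS domain in this plan.

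**Conclusion.** The point holds for the text. The prior-treatment bullet in 16.5.3 contradicts the worsening sentence in 16.5.2, and it sits badly with the causality-neutral definition in its own section. If followed as written, it lets worsened symptoms, and new ones blamed on earlier treatment, go unrecorded without trace.

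The direction of any error is known: the bullet can only remove events from the table. The size is not. The documents do not support saying that the reported rates *will* be too low, or that they would fall to the placebo level. That would need a reaction rate at this trial's doses and a share of events dropped, and neither is given. Staff who follow the worsening sentence and rarely attribute new symptoms to past treatment would lose little or nothing.

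The primary endpoint and the sample size are unaffected, and Section 11.2 sets no stopping rule that depends on event rates. Because safety is a secondary objective and the correction is short, it should be made.

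**What to change.** 1. In 16.5.3, limit the prior-treatment bullet to symptoms and signs that were present before the first CBD dose and have not increased in grade or frequency since. This brings it into line with 16.5.2.
2. State that any new or worsened symptom is recorded as an adverse event, with the investigator's view of its cause given on the 16.5.4 scale (*Unlikely* or *Unrelated* where appropriate).
3. Record the grade of ongoing symptoms before the first dose, so that worsening can be judged against something.
4. In 16.5.2, replace the pointer to Section 8.3 with 16.5.3.

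The cost is a few words in two sections, a short symptom entry at baseline, a few more low-grade adverse events on the case report form, and a slightly less favourable table. No treatment rule or planned analysis changes.

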8.1 Dose Modifications and Guidelines for Adverse Event Management

8.1.1 Dose Modifications

Dose levels:

- Dose level 1 25 mg BID
- Dose level 2 50 mg BID
- Dose level 3 75 mg BID
- Dose level 4 100 mg BID

If the dose is reduced because of toxicity, that dose should be maintained for the remainder of the trial and not re-escalated.

Toxicity Grade	What to do
Grade 1 – possibly, probably, or definitely related to study drug	For ALT/AST > 3x ULN, discontinue study medication.
	For all other grade 1 toxicities, monitor as needed until the problem has resolved (i.e., grade 0), stabilized (i.e., remains as grade 1), or is otherwise explained.
	If Grade 1 symptoms persist, the PI or Co-I will assess whether the dose should be reduced by 1 dose level or, if the patient is receiving dose level 1, whether the patient should discontinue study medication.
Grade 2 – possibly, probably, or definitely related to study drug	For total bilirubin > 2x ULN, discontinue study medication.
	For all other grade 2 toxicities, monitor as needed until the problem has resolved (i.e., grade 0), stabilized (i.e., remains as grade 1 or grade 2), or is otherwise explained.
	If Grade 2 symptoms persist, the PI or Co-I will assess whether the dose should be reduced by 1 dose level or, if the patient is receiving dose level 1, whether the patient should discontinue study medication.
Grade 3 – possibly, probably, or definitely related to study drug	If the patient was receiving dose level 1 at the time of toxicity development, the patient should discontinue study drug.
	For patients receiving dose level 2 or higher, if the symptoms resolve or improve to grade 1 or 2 within 7 days, the dose should be reduced by 1 dose level and the drug restarted at the time of symptom improvement. This dose is to be maintained if no further Grade 3 toxicity is noted.
	If the symptoms do not resolve or improve to grade 1 or 2 within 7 days, the patient can continue to hold study drug for another 7 days. If the symptoms resolve or improve to grade 1 or 2, the dose should be reduced by 1 dose level and the drug restarted at the time of symptom improvement. This dose is to be maintained if no further Grade 3 toxicity is noted. If

	the symptoms remain Grade 3 possibly, probably, or definitely related to the study drug, the patient should be permanently removed from protocol treatment.

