8.3 Contraception

Only post-menopausal women (including those rendered postmenopausal with LHRH agonist therapy) are eligible for enrollment on this clinical trial. Postmenopausal is defined as one or more of the following:

- Absence of menses for at least 12 months
- Concurrent use of LHRH agonist therapy
- Prior bilateral salpingo-oophorectomy
- Serum or plasma concentrations of estradiol within postmenopausal range according to local lab values

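### Section 16.5.3 gives two unaligned tests for laboratory abnormalities, so an asymptomatic liver-test rise that stops CBD could reasonably be left out of the adverse event report

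*Combined protocol and SAP*

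**What the plan says.** Section 16.5.3 opens with a broad definition: "An AE can be any unfavorable and unintended sign (including an abnormal laboratory finding" (the parenthesis closes there). It attaches no requirement for symptoms or treatment. Further down, in a list that mostly sets out what is not reported, a bullet reads "Abnormal laboratory values or test results constitute adverse events if they induce clinical signs or symptoms or require therapy", followed by "They are to be captured under the signs, symptoms or diagnoses associated with them".

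Section 8.1 carries the title "Dose Modifications and Guidelines for Adverse Event Management". Its table, in 8.1.1, is arranged by toxicity grade and by attribution to study drug. It contains actions that depend on a laboratory value alone, such as "For ALT/AST > 3x ULN, discontinue study medication", and a similar stop for total bilirubin above 2x ULN. Neither requires a symptom. Section 7.3.1 lists unacceptable toxicity, by reference to 8.1, as a reason for discontinuing treatment.

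Section 16.5.2 makes recording depend on the definition. It covers "All events meeting the criteria and definition of an AE or SAE, as defined in Section 8.3", and these go "on the CRF regardless of frequency, severity (grade) or assessed relationship to the study treatment". Section 8.3 is headed "8.3 Contraception". Earlier in 16.5.2, however, the reader is told correctly that the definitions follow below.

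For analysis, 12.3.2 Secondary endpoints, item 4, plans a descriptive AE report by dose. Section 11.1 names liver tests, creatinine and hemoglobin as safety data, but section 12 states no summary of them.

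**The concern.** Safety and tolerability is secondary objective 3, and 3.1.4 Clinical Safety itself lists raised transaminases, falls in hemoglobin and rises in creatinine. The stops in 8.1.1 that rest on a laboratory value alone are therefore among the safety results a reader would most want to see.

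The protocol can treat such a rise as drug-related toxicity serious enough to end treatment and still leave it open whether the rise is an AE. Two coordinators could record the same stop differently, each with a reasonable reading of 16.5.3. The narrower reading gives the lower AE count, and no planned laboratory table or table of discontinuation reasons would show the difference.

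**Working it through.** The plan states no figure on this point, so there is nothing to reproduce. The check is textual, with one calculation for scale.

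**1. Test case.** Take a woman with normal liver tests at entry. At week 4, 8 or 15 (the scheduled panels in section 9) her ALT is above 3x ULN. She has no symptoms and needs no therapy, and the rise is judged at least possibly related to CBD.

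| Text | Result for this case |
|---|---|
| 8.1.1 | CBD is stopped |
| 7.3.1 | Falls under unacceptable toxicity |
| 16.5.3, general definition | Can be an AE |
| 16.5.3, laboratory bullet | No sign, symptom or therapy, so no trigger is met |
| 16.5.3, capture sentence | May have no associated sign, symptom or diagnosis to record it under |
| 16.5.2, recording rule | AE entry on the CRF required only if the definition is met |
| 12.3.2, item 4 | Counted only if recorded as an AE |

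**2. Two readings of the bullet.**
- *Sufficient condition.* Laboratory values with symptoms or therapy are AEs, and others may be too. The case is then an AE through the general definition, but the bullet adds nothing to that definition.
- *Limiting condition.* Only laboratory values with symptoms or therapy are AEs. The bullet then does some work, and the case is not an AE.

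The wording fits the first reading. The wish to give the bullet a purpose, together with the capture sentence, favours the second. No text says which governs.

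**3. A contrast within 16.5.2.** That section treats a laboratory abnormality with onset before treatment as pre-existing, and counts any rise in toxicity grade of a pre-existing condition as an AE, with no symptom test. Section 5.2.3 excludes only ALT/AST above 3x ULN, so women may enter with milder elevations. A woman who starts mildly elevated and rises in grade is thus arguably an AE under 16.5.2. The woman in step 1, stopped for the same value, may not be.

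**4. Scale.** Inputs: n = 44 enrolled (4.2), all assumed to start CBD and to form the denominator. The exact (Clopper-Pearson) interval is my choice for illustration, since the plan asks only for descriptive statistics on AEs.
- One event: 1/44 = 2.3%.
- 0/44: upper limit = 1 − 0.025^(1/44) = 8.0%, so the interval is 0 to 8.0%.
- 1/44: lower limit = 1 − 0.975^(1/44) = 0.06%; upper limit = 97.5th percentile of Beta(2, 43) = 12.0%. The interval is 0.1 to 12.0%.

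Each omitted event therefore lowers the reported proportion by 2.3 percentage points.

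**The case against.** The strongest reply is that the bullet, taken at its word, excludes nothing. It says *if*, and the general definition expressly covers laboratory findings. Other text points the same way: 16.5.2 counts grade increases in pre-existing conditions, section 8 and 16.5.4 adopt CTCAE v5.0 for AE reporting, and the 8.1.1 rows use the attribution terms that 16.5.4 defines for AEs. Staff who apply the stop are already grading and attributing the rise as they would an AE. The list layout is also weak evidence, because the extracted text appears to have lost its indentation.

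Most of this stands. A reader might infer that 16.5.3 bars asymptomatic laboratory abnormalities from the AE record, and the documents do not go that far. What remains is that none of these passages says it prevails over the bullet, and the CTCAE text says how AEs are graded, not which laboratory values qualify.

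Three further inferences should also be resisted.
- *Staff are never sent to the right definition.* Section 16.5.2 says the definitions are below; the reference to 8.3 is a clerical slip. The text below is, however, the ambiguous text.
- *Safety data are lost.* The laboratory values are collected, 11.1 treats them as safety data, and the stop would probably be logged under 7.3.1. The risk is to the AE tabulation.
- *The drug-information table gives the number of affected women.* It shows elevated transaminases in 3% on placebo and 8% at 10 mg/kg/day, which would be 44 × 0.03 = 1.3 to 44 × 0.08 = 3.5 women. But it does not define elevated and gives no share above 3x ULN or without symptoms. Section 2.2 puts the trial doses lower, at 0.625 to 4 mg/kg/day.

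**Conclusion.** The point holds as an unresolved inconsistency in a recording rule. On a reasonable, though not compelled, reading of 16.5.3, a liver-test rise that alone stops CBD as drug-related toxicity can be left out of the only safety analysis stated in 12.3.2.

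The size is not established, because the documents give no rate for asymptomatic rises past the 8.1.1 limits at the trial doses. The 0/44 versus 1/44 contrast shows what one omission would do; it does not predict that one will occur. The primary endpoint is unaffected. The wrong section number is clerical, and the missing laboratory table on its own would be only a matter of detail. The case for acting is that secondary objective 3 needs the same event to be recorded the same way each time, and clarification costs little.

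**What to change.** Reconcile the laboratory bullet in 16.5.3 with the general definition and with 8.1.1. State that a laboratory abnormality leading to dose reduction, hold or discontinuation of CBD is recorded as an AE under its CTCAE v5.0 term, whether or not it caused symptoms or required therapy.

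Alongside this:
- In 16.5.2, change the reference to Section 8.3 so that it points to 16.5.3.
- As a minor addition to 12.3.2 Secondary endpoints, item 4, summarise descriptively the ALT, AST, bilirubin, creatinine and hemoglobin already collected (for example, change from baseline and worst post-baseline grade), and list discontinuations by reason.

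No threshold or action in section 8.1 changes, and no new test is needed: weeks 4, 8 and 15 already supply 40 × 3 = 120 panels from completers, or 44 × 3 = 132 if all women attend. The cost is an amendment for IRB review under 16.7, a few more AE records confined to laboratory values that changed CBD dosing, and one descriptive table. If women have already been treated, their laboratory-driven dose changes should be checked against the revised wording.
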